 - Endovenous glue induced thrombosis (EGIT) or endovenous heat induced thrombosis (EHIT)
 - Symptomatic deep vein thrombosis (DVT) events
7. Additional events evaluated through 60 months (through 12 months for subjects enrolled in the VenaSeal vs. Surgical Stripping Study):
 - Symptomatic pulmonary embolism (PE)
 - Serious adverse events (SAEs)

Healthcare utilization secondary endpoints

8. Number and type of adjunctive treatments conducted through 12 months post-index procedure.
9. Healthcare utilization related to the target limb VRD, as determined by the number of healthcare visits conducted, and other health-related resources utilized (e.g., home healthcare services) between study visits through 60 months (30 days, 6 and 12 months only for subjects enrolled within the VenaSeal vs. Surgical Stripping Study).
10. Procedures, tests and treatment of AEs related to the treatment modality or index procedure.
11. VLU Study: Healthcare utilization and routine wound care treatments between study visits through 60 months.

Patient Experience secondary endpoints

12. Time to return to normal activities as reported by the patients.
13. Intra-procedural and post-procedural pain at the index procedure, and 7 days and 30 days as reported by the patient using the numeric rating scale (NRS) with a scale of 0-10.
14. Change in venous disease symptoms at 7 and 30 days, and at 6, 12, 24, 36, 48, and 60 months compared to baseline (7 days, 30 days, 6 and 12 months only for subjects enrolled in the VenaSeal vs. Surgical Stripping Study), as measured by the revised Venous Clinical Severity Score (rVCSS) and subject self-reporting.

15. Change in AVVQ score at 30 days, and 6, 12, 24, 36, 48, and 60 months (30 days, 6 and 12 months only for subjects enrolled in the VenaSeal vs. Surgical Stripping Study) compared to baseline.
16. Change in EuroQoL Group 5-Dimension Self-Report Questionnaire (EQ-5D-5L) at 30 days, and 6, 12, 24, 36, 48 and 60 months (30 days, 6 and 12 months only for subjects enrolled in the VenaSeal vs. Surgical Stripping Study) compared to baseline.
17. Change in the 36-Item Short Form Health Survey (SF-36) reported by the patient at 30 days, and 6 and 12 months compared to baseline.
18. Change in the Venous Dependent Quality of Life (VenousDQoL) reported by the patient at 30 days, and 6, 12, 24, 36, 48, and 60 months (30 days, 6 and 12 months only for subjects enrolled in the VenaSeal vs. Surgical Stripping Study) compared to baseline.

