10.1. Schedule of Events and Data Collection

An overview of all data collection requirements is given in **Table 6** and **Table 7** below. All subjects (in the Randomized Studies as well as the VLU Study) will follow the assessment schedule in Table 6, and VLU Study subjects will also follow the assessment schedule in Table 7, until healing per the CIP definition has occurred. Study-specific assessments may not occur until the ICF has been obtained, and only trained/delegated personnel may conduct study specific assessments. Subjects should return to the study site for their study visits; other local hospitals or clinics should not be used as an alternative.

Some study follow-up visits are not routine care. Routine care post-procedure differs from site to site. However, follow-up visits that are not routine care are not considered burdensome and/or invasive.

VENASEAL SPECTRUM Clinical Investigation Plan

MDT18034

Version 5.0

Page 52 of 164

Medtronic

Table 6: Schedule of Assessments – All Subjects

Data Collection Requirement	Screening	Baseline (<30 days before procedure)	Index Procedure (Day 0)	Day 7 (± 2 days)	Day 30 (± 7 days)	3+ Months Adjunctive Therapy (Optional)	6 Months (± 4 weeks)	12 Months ¹ (± 8 weeks)	24, 36, 48 and 60 Months (± 8 weeks)	Unscheduled ²
Informed Consent	X									
CEAP Clinical Classification (2004 and 2020)	X					X	X	X	X	
Randomization	X									
Demographics, Medical History		X								
Concomitant Medications		X	X							
rVCSS	X			X	X		X	X	X	X
Patient-Reported Symptoms		X		X	X		X	X		
EQ-5D-5L QoL		X			X		X	X	X	
AVVQ QoL	X				X		X	X	X	
SF-36 QoL	X				X		X	X		
VenousTSQ ³					X		X	X		
Duplex Ultrasound		X ⁴	X	X	X		X	X	X	X
Procedure-related Data & Outcome			X							
Physician Satisfaction with Procedure			X							
Patient-Reported Outcomes				X	X		X	X	X	
Reintervention Review				X	X		X	X	X	
Healthcare utilization				X	X		X	X	X	
Adjunctive Therapy Assessment						X	X	X	X	
Adverse Event Assessment			X	X	X	X	X	X	X	X
Device Deficiency Assessment			X							

¹ Subjects in VenaSeal vs. Surgical Stripping Study will be followed through 12 months only.

Medtronic Business Restricted

CONFIDENTIAL

056-F275, v B Clinical Investigation Plan Template

²AE assessments at unscheduled visits are required. Additional assessments are per investigator's discretion; see section 10.11 for additional detail

³VenousTSQe captured at 30 Days; VenousTSQs captured at 30 Days, 6 Months and 12 Months

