⁴Sites to utilize their standard of care DUS to assess screening criteria, within 6 months of the Screening/Baseline visit; if not conducted in a standing position, sites will need to re-image patient for target vein measurements only

Table 7: Additional Schedule of Assessments – VLU Study

Data Collection Requirement	Screening	Baseline	Procedure	7 & 30 Days	2, 3, 4, & 5 Months (+/- 7 days)	6 Months	8 & 10 Months (+/- 2 weeks)	12 Months	24, 36, 48, & 60 Months	Healing Verification (<2 weeks of healing)
All-Subject Requirements and Visit Windows from Table 6	X	X	X	X		X		X	X	
Etiology Photograph	X									
Target Active Ulcer Assessment		X		X	X	X	X	X		
Ulcer-specific Healthcare Utilization				X	X	X	X	X	X	X
Active Ulcer or Healing Verification Photograph		X ¹		Photographs captured at each visit until healing is demonstrated through 24 months.						X ²
Adverse Event Assessment			X	X	X	X	X	X	X	X
Ulcer Healing and/or Recurrence Assessment				X	X	X	X	X	X	X
Active Ulcer Wound Care	Wound care and compression therapy to proceed per routine care until healing is demonstrated.									

¹Index procedure should occur within 7 days of baseline ulcer photograph. If the baseline visit is more than 7 days out from the index procedure, photographs should instead be taken on the day of the index procedure, prior to the start of the procedure.

²Healing verification to be captured through 24 months, as applicable.

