- Subject's healthcare utilization related to their target limb VRD, as determined by medical record review and/or subject's report of healthcare visits conducted and other health-related resources utilized (e.g. home healthcare services) between study visits.
- Procedures, tests and treatment of AEs related to the VenaSeal™ system or the index procedure, as reported by sites in AE reporting.
- VLU Study: Subject's healthcare utilization and routine wound care treatments between follow-up visits through 60 months.

VLU Assessment on the target limb

Patients who enter the study at designated VLU sites with an active VLU (CEAP 6) on the target limb will receive wound care and compression therapy per the site's standard of care for their VLUs, and undergo ulcer assessments at screening, baseline and each follow-up visit until the ulcer is healed.

At the Screening visit, after consent has been obtained, target limb ulceration will be photographed by the provided eKare imaging equipment to assess etiology and if circumferential. Any ulcer curvature around the leg that extends out of sight and that cannot be captured in a single photograph would be considered as a circumferential ulcer and such subjects will not be included in the study. These photographs captured as part of routine care within 60 days can also be utilized, as deemed appropriate by the treating physician. Photographs will be submitted to the core laboratory to assess venous etiology within 3 business days. If the core laboratory concludes that the ulcer is of non-venous etiology, then the subject will be considered as a screen failure and exited from the study. The baseline ulceration

Medtronic Business Restricted

CONFIDENTIAL

056-F275, v B Clinical Investigation Plan Template

photographs must be taken within 7 days of the index procedure. If the baseline visit is scheduled more than 7 days from the index procedure, the site may collect all remaining baseline data and hold off on taking the photographs until the day of the index procedure, prior to the start of the procedure. The baseline photographs will be sent to the core laboratory for assessments.

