Follow-up target limb ulcer assessments will take place at Day 7, Day 30, Months 2, 3, 4, 5, 6, 8, 10, and 12 or until healing has occurred. If the healing has not occurred at 12 months, subjects will revert to the annual visit schedule and continue to follow standard wound care unless healing occurs, and a healing verification visit is necessary. If healing occurs past 24 months, subjects will no longer undergo a healing verification visit. When all target limb ulceration has healed, subjects will have an ulcer healing verification visit (up to 24 months) as outlined in section 10.12.

Photographs will be taken of active ulcers and at the healing verification visit using the eKare insight® 3D wound imaging system provided to VLU sites. Multiple photographs will be captured: 1) one 3-dimensional photo for the measurements and 2) a standard, 2-dimensional photo of a wider view of the index limb. The ulcer size will be assessed, and complete healing will be confirmed by the wound core laboratory via these photographs provided by the study site. Core laboratory assessment is also described in section 13.3.

If the ulcer on the target limb recurs, this will be reported in the CRF during study follow-up visits. The ulcer status compared to the last study visit (e.g., healed, recurred, or healed and recurred) will be collected at each visit. In addition, type of the wound care received since last visit including debridement, skin graft, dressing change, Unna boots or any other treatment will be recorded in the CRFs at each follow-up visit until initial ulcer healing is confirmed. An ulcer core laboratory manual and site training will be provided to sites for further details on the photograph process.

New ulcers not related to the original ulceration that develop post-index procedure but prior to initial healing may need to be reported as AEs (if considered worsening of disease) and will undergo ulcer assessments as described here for all ulcers. New ulceration that develops following healing confirmation will be considered ulcer recurrence and will not be assessed as described here, however may need to be reported as AEs.

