7.9.2.5 Healthcare utilization secondary endpoints

The following healthcare utilization secondary endpoint data will be collected:

1. Number and type of adjunctive treatments conducted through 12 months post-index procedure.

Endpoint Definition

Rate of adjunctive procedures, phlebectomy or sclerotherapy, for varicosity on the target limb through 12 months post index procedure.

Analysis Methods

The number and rate of adjunctive procedures through 12 months will be estimated. To calculate the rate, the numerator is the count of adjunctive procedures. The denominator is the number of person-years of follow-up. The amount of follow-up per person is defined as their date of exit or last known follow-up or the date of their 12 month follow-up visit (whichever is first) minus their date of index procedure. A similar estimate will be constructed for the type of adjunctive procedure, phlebectomy or sclerotherapy.

Determination of Subjects for Analysis

ITT population.

2. Healthcare utilization related to the target limb Venous Reflux Disease (VRD), as determined by the number of healthcare visits conducted between study visits through 60 months.

Endpoint Definition

Rate of healthcare utilization visits related to venous reflux disease.

Analysis Methods

The number and rate of healthcare utilization visits will be estimated. To calculate the rate, the numerator is the count of HCU visits. The denominator is the number of person-years of follow-up. The amount of follow-up per person is defined as their date of exit or last known follow-up minus their date of index procedure. A similar estimate will be constructed within the HCU type of interest (Inpatient, Outpatient, Clinic, Outpatient ER visits).

Determination of Subjects for Analysis

ITT population

3. Procedures, tests, and treatment of AEs related to the treatment modality or index procedure through 60 months.

Endpoint Definition

Healthcare utilization measured by number of healthcare resources utilized for treatment of adverse events, including hospitalization, prolongation of hospitalization, actions taken or diagnostic tests performed.

Analysis Methods

A listing will be provided per adverse event of the actions taken.

Determination of Subjects for Analysis

ITT population

4. Healthcare utilization and routine wound care treatments between study visits through 60 months.

Endpoint Definition

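### Itemised wound care is recorded only until first ulcer healing, but the VLU wound-care endpoint is defined through 60 months, so its later counts may miss care for recurrent ulcers

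*Protocol*

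**What the plan says.** The endpoint runs to 60 months in three places:

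- Protocol 5.2.3, secondary endpoint 11: "VLU Study: Healthcare utilization and routine wound care treatments between study visits through 60 months".
- Protocol 10.5, Healthcare Utilization: "VLU Study: Subject's healthcare utilization and routine wound care treatments between follow-up visits through 60 months".
- SAP 7.9.2.5 item 4: "Healthcare utilization and routine wound care treatments between study visits through 60 months". The SAP defines this as the type of wound care (debridement, skin graft, dressing change, Unna boots or other) and its quantity. It is summarised as counts by type per study visit in the ITT population, with no cut-off at healing.

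The collection rules stop earlier:

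- Protocol 10.5, VLU Assessment on the target limb, lists the same kinds of wound care and says they "will be recorded in the CRFs at each follow-up visit until initial ulcer healing is confirmed".
- The same subsection adds: "New ulceration that develops following healing confirmation will be considered ulcer recurrence and will not be assessed as described here".
- Protocol 10.1: "VLU Study subjects will also follow the assessment schedule in Table 7, until healing per the CIP definition has occurred".
- The visit lists in Protocol 10.10 put ongoing wound care under active ulcers. Once healing is confirmed, the VLU item is recurrence status.

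Table 7 in Protocol 10.1 nevertheless marks the row "Ulcer-specific Healthcare Utilization" at 24, 36, 48 and 60 months.

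**The concern.** The items in the stop rule are the items that the SAP counts. If recording ends at the first confirmed healing, a later visit with no wound-care entry can mean that no care was given or that the form did not ask for it. The output would be labelled as covering 60 months, while for a healed subject it covered only the period to first healing.

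This matters because the plan expects recurrences: ulcer recurrence and ulcer-free time are themselves VLU endpoints through 60 months. Utilization data also feed the sponsor's health-economic work (Protocol 14.6, SAP 7.11). Itemised care that was not recorded at the time is hard to reconstruct later.

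**Working it through.** The plan states no figure for wound-care use or ulcer recurrence, so there is nothing to reproduce. The main check sets the rules side by side.

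1. **Same variable.** Protocol 10.5 and SAP 7.9.2.5 item 4 list the same wound-care types, so the stop rule governs the variable the endpoint needs.
2. **Different horizons.** The stop rule ends at initial healing. Endpoint 11, the utilization statement in 10.5 and the SAP end at 60 months. Both cannot hold for a subject who heals and then recurs.
3. **The schedule does not settle it.** Section 10.1 applies Table 7 until healing, but Table 7 marks ulcer-specific utilization through 60 months. Protocol 10.12 lists ongoing wound care and ulcer-specific utilization as separate items, so the Table 7 mark does not clearly include wound-care type.
4. **Other routes.** General utilization since the last visit is collected at every scheduled visit (10.10), but SAP 7.9.2.5 item 2 analyses it as healthcare visits by setting. Treatment of a recurrence reported as an adverse event is recorded (12.3), but that reporting is conditional in 10.5, and SAP item 3 outputs it as a listing. Neither feeds the counts in item 4.

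**Illustration 1: how long itemised recording lasts.** Inputs: the exponential healing assumption with a 70-day median (Protocol 14.2.1) and a 1825-day horizon (Table 8). Dropout and any lag to confirmation are ignored.

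- λ = ln 2 / median; expected window = (1 − exp(−1825λ)) / λ.
- Median 70 days: λ = 0.6931 / 70 = 0.0099 per day; window = 101 days; 101 / 1825 = 5.5% of follow-up.
- Median 56 days (the reference trial's early-intervention group): 81 days, or 4.4%.
- Median 180 days (assumed): 260 days, or 14.2%.

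This is the share of follow-up time covered, not the share of care lost.

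**Illustration 2: subjects affected.** Cumulative recurrence of 10% to 50% is assumed. 0.10 × 125 = 12.5 and 0.50 × 125 = 62.5, so about 13 to 63 subjects.

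**Illustration 3: open-ulcer time.** A simulation of alternating open and healed periods used the 70-day median for every ulcer, no dropout or death, and assumed recurrence of 5%, 10% or 20% per year after healing. Mean first-ulcer time is 101 days. Mean later open time is 22, 44 or 85 days:

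- 22 / (101 + 22) = 18%
- 44 / (101 + 44) = 30%
- 85 / (101 + 85) = 46%

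These are shares of open-ulcer days under assumed recurrence rates. The SAP reports counts per visit, so they are not the error in any planned output.

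**The case against.** A reader might infer that all care for recurrent ulcers is lost. The documents do not support that. Healthcare utilization since the last visit is required at every scheduled visit through 60 months, healed or not, including the remote 48- and 60-month visits, and 10.5 describes it as visits plus other resources such as home care. Target-limb adverse events are reportable with the action taken. Subjects whose ulcers never heal are not cut off by the stop rule.

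The wording on healing can also be read more kindly. Read literally, section 10.1 would end the recurrence row of Table 7 too, yet 10.12 continues recurrence data through 60 months. Table 7 drops the active-ulcer assessment at 24 to 60 months but keeps ulcer-specific utilization, which suggests that the latter was meant to continue. The sentence excluding recurrences from assessment follows one about ulcer assessments and may not concern utilization at all. Protocol 14.6 covers all ulcers on the target limb but refers to wound care through ulcer healing, which is at least compatible with a stop.

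All of this limits the point. It does not remove it: the explicit rule for recording wound-care type still ends at initial healing, and none of the other routes supplies the SAP's counts by type. If Table 7 was meant to prevail, sites have to guess that, and they may guess differently.

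**Conclusion.** The collection rule and the endpoint contradict each other for one component, itemised wound care after first healing. Followed as written, the plan does not require that component for recurrent ulcers, so the per-visit counts after first healing may be too low and their zeros cannot be interpreted. This is one descriptive secondary endpoint in a single-arm study with no hypothesis test.

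The size of the shortfall is unknown. It depends on the recurrence rate, on how sites read Table 7 and on how much care each recurrence needs, none of which the documents give.

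Two further inferences are not supported. One is that total 60-month utilization is understated by a stated percentage: the percentages above rest on assumed recurrence rates and on open-ulcer time as a stand-in for care. The other is that the omission favours the device: the VLU Study has no comparator, and the economic analysis is in a separate plan, so the direction and size of any effect on the cost model cannot be established here.

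**What to change.** Reconcile Protocol 10.1 (text and Table 7), both statements in 10.5, the visit lists in 10.10, and SAP 7.9.2.5 item 4. The preferred changes are:

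- **Protocol 10.5:** record wound-care type at each scheduled visit through 60 months whenever any target-limb ulcer, including a recurrence, has been open since the last visit.
- **Protocol 10.1:** limit the until-healing condition to the extra visits at months 2 to 10 and the core-laboratory photographs.
- **Protocol 10.10:** add wound care since the last visit to the post-healing item when a recurrence is reported.
- **SAP 7.9.2.5 item 4:** report wound care before first healing and after recurrence separately.

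If the sponsor does not want these data, the alternative is to relabel the wound-care component in endpoint 11 and the SAP as running through initial healing.

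The cost is minor amendment wording and some added data entry at visits where recurrence status is already collected. No visit or imaging is added. Whether the existing CRF page can be reused must be checked, since the CRFs are not in the documents. The change concerns data collection only, not how wounds are managed.

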10.6. Screening

During the screening visit, the site will conduct the following:

1. Informed consent.
2. Subject evaluation for inclusion/exclusion criteria: Sites should utilize their routine care diagnostic DUS from within 6 months of the screening visit, or repeat this DUS if greater than 6 months old.

3. CEAP clinical classification.
4. VLU Study: Photographs to assess ulcer venous etiology and exclude circumferential ulcers. These photographs captured as part of routine care within 60 days can also be utilized as deemed appropriate by treating physician. Photos must be submitted to the core laboratory and confirmed as venous etiology prior to moving on to the Baseline visit.

Sites may randomize the patients in the Randomized Studies following the Screening Visit data collection and confirmation of inclusion/exclusion criteria.

10.7. Prior and Concomitant Medications

The current use of the following medications will be collected at the Baseline visit:

1. Anticoagulants (e.g., Warfarin, NOAC, Lovenox)
2. Antiplatelets/Aspirin/P2Y₁₂-inhibitors
3. Non-Steroidal Anti-Inflammatory Drugs (NSAIDs)
4. Other pain medication.

Medications given as part of the index procedure will also be documented. Medications used for treatment of any AEs will be tracked during the AE assessment. Additional concomitant medications will not be recorded for study purposes.

10.8. Baseline (within 30 days prior to index procedure)

The Baseline visit may be combined with the index procedure visit if the site chooses, so long as the Baseline data is collected prior to the index procedure.

VLU Study: wound care and compression therapy should be initiated per the site's standard of care and as early as possible (e.g., after confirmation of venous etiology by the core laboratory), if it is not ongoing already.

During the Baseline visit, the site will collect the following:

1. Demographics, as able to be collected per the site's regional regulations.
2. Targeted medical history and concomitant medications, limited to items potentially related to the subject's VRD as indicated in the CRF specifications provided separately.
3. Baseline DUS: If routine care DUS was not conducted in a standing position, sites will need to re-image patient for target vein measurements only.
4. rVCSS
5. AVVQ QoL questionnaire

6. EQ-5D-5L QoL questionnaire
7. SF-36 QoL questionnaire
8. Venous DQoL
9. Patient-reported symptoms and indication of their dominant symptom.
10. VLU Study: Ulcer assessment on target limb including ulcer photograph for submission to core laboratory. The baseline ulcer photograph must be taken within 7 days prior to the index procedure. If the Baseline visit is more than 7 days prior to the index procedure, then photographs should be collected at the index procedure before the start of the procedure.

